## **6.5 SAFETY ANALYSES**

Safety analyses will include all patients who receive at least one dose of study drug (GDC-0853 or placebo) with patients grouped according to the treatment they received.

Safety will be assessed through summaries of adverse events, laboratory test results, ECGs, and vital signs. Verbatim descriptions of treatment-emergent adverse events will be coded, and their incidence will be summarized by treatment arm. A treatment-emergent adverse event is defined as any new adverse event reported or worsening of an existing condition on or after the first dose of study drug during AE reporting period. In addition, separate summaries will be generated for serious adverse events, AESI, deaths, pregnancies, malignancies, adverse events leading to discontinuation from the study, and adverse events leading to discontinuation of study drug.

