### **5.3.1 Adverse Event Reporting Period**

Investigators will seek information on adverse events at each patient contact. All adverse events, whether reported by the patient or noted by study personnel, will be recorded in the patient's medical record and on the Adverse Event eCRF.

**After informed consent** has been obtained **but prior to initiation of study drug**, only serious adverse events caused by a protocol-mandated intervention (e.g., invasive

procedures such as biopsies, discontinuation of medications) should be reported (see Section 5.4.2 for instructions for reporting serious adverse events).

**After initiation of study drug**, all adverse events will be reported until 8 weeks after the last dose of study drug the patients receives, either in this study or in an OLE, if initiated.

Instructions for reporting adverse events that occur after the adverse event reporting period are provided in Section 5.6.

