### **5.4.2.2 Events That Occur after Study Drug Initiation**

After initiation of study drug, serious adverse events and adverse events of special interest will be reported until 8 weeks after the last dose of study drug the patients receives, either in this study or an OLE, if initiated. Investigators should record all case details that can be gathered immediately (i.e., within 24 hours after learning of the event) on the Adverse Event eCRF and submit the report via the electronic data capture (EDC) system. A report will be generated and sent to Safety Risk Management by the EDC system.

In the event that the EDC system is unavailable, the Serious Adverse Event/Adverse Event of Special Interest Reporting Form provided to investigators should be completed and submitted to the Sponsor or its designee immediately (i.e., no more than 24 hours after learning of the event), either by faxing or by scanning and emailing the form using the fax number or email address provided to investigators. Once the EDC system is available, all information will need to be entered and submitted via the EDC system.

Instructions for reporting serious adverse events that occur after the last dose of study treatment are provided in Section 5.6.

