### **5.6 ADVERSE EVENTS THAT OCCUR AFTER THE ADVERSE EVENT REPORTING PERIOD**

The Sponsor should be notified if the investigator becomes aware of any serious adverse event that occurs after the end of the adverse event reporting period (defined as 8 weeks after the last dose of study drug the patients receives, either in this study or an OLE, if initiated), if the event is believed to be related to prior study drug treatment. These events should be reported through use of the Adverse Event eCRF. However, if the EDC system is not available, the investigator should report these events directly to the Sponsor or its designee, either by faxing or by scanning and emailing the Serious Adverse Event/Adverse Event of Special Interest Reporting Form using the fax number or email address provided to investigators.

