c Week 48 visit is the last day of the study treatment period; however, no blinded study drug will be given at the Week 48 visit. The last dose of blinded study drug is the p.m. dose (evening) prior to the Week 48 visit. If eligible, patients may enroll into the open-label extension Study GA30066 to receive

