## Appendix 1 Schedule of Activities (cont.)

---

their first open-label dose of GDC-0853 on Day 1 of Study GA30066 (after a trough PK level is drawn) or they will proceed to the SFU period and return for the SFU visit on Week 56 (8 weeks after last dose of study drug). For patients enrolling into the OLE Study GA30066, Day 1 is the same day as the Week 48 visit of Study GA30044.

- d At an unscheduled visit (UV), adverse events and concomitant medications must be assessed. All other assessments are to be performed only if medically indicated based on the reason for the UV. If the patient returns for an unscheduled visit *or regular study visit* and has any evidence of increased SLE-activity requiring treatment, perform assessments required for a flare visit (FV).
- e A flare visit (FV) is any unscheduled visit where the patient *may* require escalation of treatment for increased SLE activity. *Assessments are to be performed only if medically indicated based on the reason for the FV.*
- f Patients will receive a telephone call from study staff to follow up for assessment of adverse events.
- g Either the ACR or SLICC diagnostic criteria for SLE may be used at screening to determine study inclusion.
- h Starting at the screening period, all patients must record their actual OCS use on a weekly basis and as instructed by study staff (see Section 4.3.2.4).
- i The OCS taper windows occur during Weeks 0-12 and Weeks 24-36 (tapering may be initiated after the Week 24 assessments are completed). For complete instructions on OCS tapering, see Section 3.3.6 and Appendix 4.

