- j After informed consent has been obtained but prior to initiation of study drug, only serious adverse events caused by a protocol-mandated intervention should be reported. After initiation of study drug, all adverse events will be reported until 8 weeks after the last dose of study drug. After this period, the Sponsor should be notified if the investigator becomes aware of any serious adverse event that is believed to be related to prior study drug treatment (see Section 5.6). The investigator should follow each adverse event until the event has resolved to baseline grade or better, the event is assessed as stable by the investigator, the patient is lost to follow-up, or the patient withdraws consent. Every effort should be made to follow all serious adverse events considered to be related to study drug or trial-related procedures until a final outcome can be reported.
- k Includes respiratory rate, pulse rate, temperature, and systolic and diastolic blood pressures while the patient is in a seated position for at least 5 minutes.
- l Include an evaluation of the head, eyes, ears, nose, and throat, and the cardiovascular, dermatological, musculoskeletal, respiratory, gastrointestinal, genitourinary, and neurological systems. Any abnormality identified at baseline should be recorded on the General Medical History and Baseline Conditions eCRF. Particular attention should be given to evaluation of potential manifestations of active SLE (see Appendix 9 BILAG 2004 Index; Appendix 10, SLEDAI-2K; Appendix 14, CLASI; and Appendix 13, 28-Joint Counts, Appendix 11, SFI) and of infections or other medical conditions, which could place the patient at increased risk.
- m Limited, efficacy assessment-directed or symptom-directed physical examinations should be performed *that also allow for completion of SLEDAI-2K and BILAG-2004 assessments*. Changes from baseline abnormalities should be recorded in patient notes. New or worsened clinically significant abnormalities should be recorded as adverse events on the Adverse Event eCRF.

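### Section 6.5 ends treatment-emergent AEs only at an AE reporting period that runs into the open-label extension, so events on open-label GDC-0853 can be counted under placebo

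*Combined protocol and SAP*

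**What the plan says.** Section 6.5 gives treatment-emergent AEs a start and one end bound: they are new or worsened events "on or after the first dose of study drug during AE reporting period". Of these events it says that "their incidence will be summarized by treatment arm".

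The reporting period is set elsewhere:

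- Section 5.3.1 collects AEs "until 8 weeks after the last dose of study drug the patients receives, either in this study or in an OLE".
- Section 5.4.2.2 uses nearly the same words for serious events and events of special interest.
- Section 5.6 states the end as a definition: "defined as 8 weeks after the last dose of study drug the patients receives, either in this study or an OLE, if initiated".
- Appendix 1, footnote j, leaves out the OLE: "After initiation of study drug, all adverse events will be reported until 8 weeks after the last dose of study drug".

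Footnote c of Appendix 1 fixes the handover. "The last dose of blinded study drug is the p.m. dose (evening) prior to the Week 48 visit", and "For patients enrolling into the OLE Study GA30066, Day 1 is the same day as the Week 48 visit of Study GA30044". Rollover patients receive their first open-label GDC-0853 on that day.

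**The concern.** The reporting-period text consists of collection rules, and as collection rules they are reasonable. The difficulty is that Section 6.5 borrows their end point as its analysis window and then counts by arm. A patient randomized to placebo who enters the OLE takes GDC-0853 from the Week 48 visit, inside that window. An event in those weeks meets the definition and, if arm means randomized arm, falls in the placebo column.

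If GDC-0853 raises the risk of an event, this adds active-drug events to the comparator and pulls any ratio between arms toward 1. It matters most for the separately summarized categories (serious events, events of special interest, malignancies, deaths), where one or two patients among about 80 are visible.

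**Working it through.** **Calendar.** Section 3.2.1 gives a maximum of 61 weeks on study: 35/7 + 48 + 8 = 61, which reproduces. In Appendix 1, Week 48 is Day 48×7+1 = 337 and Week 56 is Day 56×7+1 = 393. The difference is 56 days, or 8 weeks.

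**Overlap for a rollover patient.**

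- Sections 5.3.1, 5.4.2.2 and 5.6 as written: all open-label treatment plus 8 weeks. The documents do not give the OLE's length.
- Footnote j, taking the last dose in this study: up to about 8 weeks, because the last blinded dose is the evening before Week 48 and open-label dosing starts on the Week 48 visit. That is 8/56 = 14.3% of the window.

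**Whether other text closes the gap.**

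- Section 6.2 cuts the final analysis at patient or study discontinuation. Completing Week 48 and rolling over is neither, and an early rollover's 8 weeks can pass before the study ends.
- Section 6.5 groups patients by treatment received. This works at patient level; a placebo rollover has received both treatments, and no rule is given for changing columns.
- Section 4.4 ends the concomitant-medication period at OLE entry if that comes first. No such stop is written for AEs.

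**Size, by illustration.** The documents give neither AE rates nor a rollover share. Assumed inputs: constant hazards of 0.10 per year on placebo and 0.20 on drug, equal rollover of 60-85% in both arms, rollover unrelated to AEs, and 8 weeks of overlap at the drug hazard. Cumulative incidence = 1 − exp(−Σ hazard × time).

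Blinded 48 weeks only:

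- Placebo: 1 − exp(−0.10×48/52) = 8.8%
- Drug: 1 − exp(−0.20×48/52) = 16.9%
- Ratio 1.91, difference 8.0 points

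Rollover patients with the overlap counted:

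- From placebo: 1 − exp(−0.10×48/52 − 0.20×8/52) = 11.6%
- From drug: 1 − exp(−0.20×56/52) = 19.4%

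Arm totals weight these by the rollover share:

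| Window | Placebo | Drug | Ratio | Difference (points) |
|---|---|---|---|---|
| 48 weeks only | 8.8% | 16.9% | 1.91 | 8.0 |
| Overlap, others to Week 48, 60% rollover | 10.5% | 18.4% | 1.75 | 7.9 |
| Overlap, others to Week 48, 85% rollover | 11.2% | 19.0% | 1.70 | 7.8 |

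If non-rollovers are followed to Week 56, the ratio is 1.69-1.76 and the difference 7.8-8.3 points, depending on whether the drug arm's off-drug hazard is 0.10 or 0.20.

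Per 80 placebo patients, 8.4-8.9 have an event. Of these, 1.3-1.9 have their first event on open-label drug, and 0.7-0.9 exceed what the placebo hazard would give in those 8 weeks.

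Sensitivity, non-rollovers to Week 48: with a hazard ratio of 1.5 the risk ratio goes from 1.47 to 1.40-1.38; with a hazard ratio of 3, from 2.74 to 2.33-2.20.

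**Effect of a cut at OLE entry.** Rollovers then have about 48 weeks and others up to 56. Equal rollover of 60-85% gives ratios of 1.85-1.91. Unequal rollover (60% in one arm, 85% in the other) with no drug effect (0.10 throughout) gives 0.96 or 1.04. Unequal rollover is plausible, because Table 4, footnote a, bars patients who stop study drug for an AE from the OLE.

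**The case against.** The strongest reply is that rollover data naturally stop at Week 48. Section 3.1.1 sends a patient either to the Week 56 visit or to the OLE. Section 3.2.1 qualifies the 61 weeks for those who enrol in an OLE. Section 3.2.2 lists the last OLE enrolment among the end-of-study events. The OLE is a separate study, GA30066. The only scheduled GA30044 visit after Week 48 is Week 56, the alternative to rollover. On this view the OLE wording only carries safety reporting across to the next study, and the overlap is zero. Section 6 also defers details of statistical methods to the DAP, where such a cut-off could sit.

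Much of this stands. It is a plausible reading of intent, and it rules out claiming that every reading of the plan leaves an overlap; footnote j is only the narrowest written collection rule. But the reader has to infer the stop, since no section applies it to AEs. If the DAP does set a cut, the definition in Section 6.5 still needs to agree with it.

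It is also fair that Section 6.5 plans descriptive incidence with no ratio and no test, that every input to the illustration is assumed, and that the model ignores any link between rollover and AEs.

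**Conclusion.** The point holds as a defect in a stated rule: the end bound in Section 6.5, followed as written, lets open-label events into the placebo column. It is minor. On the assumed inputs the ratio drops from 1.91 to about 1.70-1.75, the absolute difference barely moves, and the excess is under one patient per 80. If GDC-0853 adds no risk there is no dilution. Unblinded committee review during the blinded period is unaffected.

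A reader might infer that the sponsor plans to place OLE events under placebo, or to pool the whole OLE into this study's tables, with larger effects. The documents do not support either: no section says so, and the study structure points the other way. What is established is that the written definition permits the error and that the available text does not exclude it.

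**What to change.** In Section 6.5 and the DAP, state that for GA30044 arm comparisons the treatment-emergent window ends at the earlier of the first open-label dose and 8 weeks after the last blinded dose, mirroring the stop in Section 4.4. Because follow-up then differs between rollovers and others, and entry to the OLE depends partly on AEs, also give the arm comparison through Week 48 or exposure-adjusted rates.

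Leave AE collection in Sections 5.3.1, 5.4.2.2 and 5.6 unchanged, and leave events after the first open-label dose to GA30066 reporting.

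The cost is two or three sentences, one extra table or set of rates, and a slightly shorter window for rollover patients. No data collection changes.

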## **6.6 PHARMACOKINETIC ANALYSES**

The PK analyses will include *tabulation of plasma concentration data and summarization of plasma concentrations by visits, with patients grouped according to treatment received. Descriptive summary statistics will include the arithmetic mean, median, range, SD, and coefficient of variation, as appropriate.*

The extent of inter-patient variability will be evaluated, and potential sources of variability *may* be assessed. Relationships between PK and PD, efficacy, and safety endpoints *may* be explored.

Additional PK analyses will be conducted during and/or at the end of the study as appropriate *and may be reported separately.*

## **6.7 BIOMARKER ANALYSES**

PD biomarkers (e.g., but not limited to CCL3, CCL4, and plasmablast signature) will *be analyzed to assess the pharmacological activity and mechanism of action of GDC-0853 in patients with moderate to severe active SLE. Data will be summarized by absolute levels of the biomarker, as well as absolute and relative changes from baseline levels for each treatment group. Additional PD analyses may be conducted as appropriate.*

## **6.8 INTERIM ANALYSIS**

An interim analysis will be performed after 50–80 patients in each of treatment arm have completed their 24-week SRI-4 response evaluation. The purpose of the interim analysis is to conduct a preliminary benefit-risk assessment of GDC-0853 treated arms compared with the placebo-treated arm and enable potential stopping for futility and/or safety concerns or to potentially inform the clinical development plan for GDC-0853. The

interim analysis will be performed and interpreted by the IMC in conjunction with a Scientific Oversight Committee who will be unblinded at the treatment group level. Additional personnel, such as Clinical Pharmacology *and biomarker* scientists, may be unblinded in order to prepare additional data displays relevant for IMC and Scientific Oversight Committee review.

The study will continue to enroll while the interim analysis is being performed. If the interim analysis indicates that one of the two dose levels of GDC-0853 does not have an appropriate safety profile or meets futility criteria as defined in the interim analysis plan in the DAP which will be written prior to conducting the interim analysis, the Sponsor may discontinue enrollment into that dose arm and switch patients to the other dose arm for the remainder of the study. The Sponsor may also elect to amend the protocol to change the dose level of GDC-0853.

Given the hypothesis-generating nature of this study, the Sponsor may choose to conduct an additional efficacy interim efficacy analysis in order to further guide internal decision making around issues such as the adequacy of dose ranging, the adequacy of sample sizes for safety and/or efficacy analyses, or to inform the clinical development plan for GDC-0853. The study will not be stopped for any other reason other than futility or safety concerns at the time of the interim analysis. The interim analysis will be performed and interpreted by the IMC in conjunction with a Scientific Oversight Committee who will be unblinded at the treatment group level. Additional personnel, such as Clinical Pharmacology *and biomarker* scientists, may be unblinded in order to prepare additional data displays relevant for IMC and Scientific Oversight Committee review. The decision to conduct an additional interim analysis and the timing of the analysis will be documented in the Sponsor's trial master file and updated DAP prior to the conduct of the interim analysis.

Further details about the interim analyses, including the IMC and Scientific Oversight Committee responsibilities and decision criteria, will be specified in the IMC and Scientific Oversight Committee Charter.

## **7. DATA COLLECTION AND MANAGEMENT**

### **7.1 DATA QUALITY ASSURANCE**

The Sponsor will be responsible for data management of this study, including quality checking of the data. Data entered manually will be collected via EDC through use of eCRFs. Sites will be responsible for data entry into the EDC system. In the event of discrepant data, the Sponsor or its designee will request data clarification from the sites, which the sites will resolve electronically in the EDC system.

The Sponsor or functional service provider will produce an EDC Study Specification document that describes the quality checking to be performed on the data. Central laboratory data and any other electronic data will be sent directly to the Sponsor, using

the Sponsor's standard procedures to handle and process the electronic transfer of these data.

eCRFs and correction documentation will be maintained in the EDC system's audit trail. System backups for data stored by the Sponsor and records retention for the study data will be consistent with the Sponsor's standard procedures.

PRO data will be collected on paper questionnaires. The data from the questionnaires will be entered into the EDC system by site staff.

## **7.2 ELECTRONIC CASE REPORT FORMS**

eCRFs are to be completed through use of a Sponsor-designated EDC system. Sites will receive training and have access to a manual for appropriate eCRF completion. eCRFs will be submitted electronically to the Sponsor and should be handled in accordance with instructions from the Sponsor.

All eCRFs should be completed by designated, trained site staff. eCRFs should be reviewed and electronically signed and dated by the investigator or a designee.

At the end of the study, the investigator will receive patient data for his or her site in a readable format on a compact disc that must be kept with the study records. Acknowledgement of receipt of the compact disc is required.

## **7.3 SOURCE DATA DOCUMENTATION**

Study monitors will perform ongoing source data verification to confirm that critical protocol data (i.e., source data) entered into the eCRFs by authorized site personnel are accurate, complete, and verifiable from source documents.

Source documents (paper or electronic) are those in which patient data are recorded and documented for the first time. They include, but are not limited to, hospital records, clinical and office charts, laboratory notes, memoranda, PROs, evaluation checklists, pharmacy dispensing records, recorded data from automated instruments, copies of transcriptions that are certified after verification as being accurate and complete, microfiche, photographic negatives, microfilm or magnetic media, X-rays, patient files, and records kept at pharmacies, laboratories, and medico-technical departments involved in a clinical trial.

Before study initiation, the types of source documents that are to be generated will be clearly defined in the Trial Monitoring Plan. This includes any protocol data to be entered directly into the eCRFs (i.e., no prior written or electronic record of the data) and considered source data.

Source documents that are required to verify the validity and completeness of data entered into the eCRFs must not be obliterated or destroyed and must be retained per the policy for retention of records described in Section 7.5.

To facilitate source data verification, the investigators and institutions must provide the Sponsor direct access to applicable source documents and reports for trial-related monitoring, Sponsor audits, and IRB/EC review. The study site must also allow inspection by applicable health authorities.

#### **7.4 USE OF COMPUTERIZED SYSTEMS**

When clinical observations are entered directly into a study site's computerized medical record system (i.e., in lieu of original hardcopy records), the electronic record can serve as the source document if the system has been validated in accordance with health authority requirements pertaining to computerized systems used in clinical research. An acceptable computerized data collection system allows preservation of the original entry of data. If original data are modified, the system should maintain a viewable audit trail that shows the original data as well as the reason for the change, name of the person making the change, and date of the change.

